1.3 Patient Population

Patient population 1: Patients with intracranial neoplasms (glial or metastatic disease) with concern for recurrence or progression on conventional imaging (e.g., MRI). This population will be broken into three groups:

1. Recurrent metastatic lesions
2. Recurrent high-grade gliomas (Grades 3 and 4)
3. Recurrent low-grade gliomas (Grades 1 and 2)

Patient population 2: Patients with suspected glial neoplasms (Grade 2-4) planning to undergo biopsy or surgery prior to primary treatment (radiation therapy and/or surgery).

2 Objectives of the Study

2.1 Primary Objective

| Primary Objective | Endpoints | Time Frame |
|--|---|-----------------|
| 1. To determine if FET PET can differentiate between benign treatment-related changes (TRC) and recurrent glioma in comparison to a composite standard of truth (CSOT) that includes pathology and other clinical information, evaluated using estimates of sensitivity and specificity. | 
• Sensitivity of FET PET using a CSOT (subject-level)• Specificity of FET PET using a CSOT (subject-level) | Up to 6 months. |

2.2 Secondary Objectives

| Secondary Objectives | Endpoints | Time Frame |
|--|---|-----------------|
| 1. To determine if FET PET can differentiate between benign TRC and recurrent glioma in comparison to a histopathological standard of truth. | 
 • Sensitivity of FET PET using a histopathology standard of truth (subject- and lesion-level) • Specificity of FET PET using a histopathology standard of truth (subject and lesion-level) • Positive Predictive Value (PPV) of FET PET using a histopathology standard of truth (subject and lesion-level) • Negative Predictive Value (NPV) of FET PET using a histopathology standard of truth (subject and lesion-level) • Accuracy of FET PET using a histopathology standard of truth (subject and lesion-level) • Misclassification Rate of FET PET using a histopathology standard of truth (subject and lesion-level) | Up to 6 months. |
| 2. To determine if FET PET can differentiate between benign TRC and recurrent glioma in comparison to a CSOT evaluated using estimates other than subject-based sensitivity and specificity. | 
 • Sensitivity of FET PET using a CSOT (lesion-level) • Specificity of FET PET using a CSOT (lesion-level) • PPV of FET PET using a CSOT (subject and lesion-level) • NPV of FET PET using a CSOT (subject and lesion-level) • Accuracy of FET PET using a CSOT (subject and lesion-level) • Misclassification Rate of FET PET using a CSOT (subject and lesion-level) | Up to 6 months. |

| Secondary Objectives | Endpoints | Time Frame |
|---|--|-----------------|
| 3. To assess the safety of FET PET, as determined by treatment emergent adverse events (TEAEs) within 48 hours of FET administration. | Incidence of treatment-emergent adverse events (TEAEs) | Up to 48 hours. |
| 4. To describe the inter-reader variability between 3 independent blinded readers of FET PET images in their assessments of benign TRC versus recurrent glioma. | Fleiss' kappa | N/A |
| 5. To describe intra-reader variability between 3 independent blinded readers of FET PET images in their assessments of benign TRC versus recurrent glioma. | Cohen's kappa | N/A |

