3.6 Duration of Follow Up

Patients will be in follow-up until their planned biopsy or surgery is performed to correlate imaging findings with histology. Follow-up will be performed off study, and there are no study specific related procedures that are required after the imaging study. If patients do not undergo biopsy or surgery, we will review imaging that was performed as clinical standard of care to determine if the lesion has grown as part of the secondary aims.

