5.2.1 Other Modalities or Procedures

5.2.1.1 PET Imaging

Participants may undergo sedation as required in order to successfully undergo imaging. Sedation or anesthesia will be administered per institutional protocol.

Study participants will undergo the FET PET imaging after all screening and baseline assessments have been completed. The radiopharmaceutical will be administered while the

patient is in the PET scanner, and imaging will last for 40 minutes. Acquired PET data will be reconstructed so that three time points are created:

1. Perfusion: 60-second acquisition that starts immediately when activity is noted in the field of view.
2. Equilibrium: 10-minute acquisition acquired between 10 and 20 minutes after injection.
3. Washout: 10-minute acquisition acquired between 30 and 40 minutes after injection.

Additionally, a 20 minute acquisition will be reconstructed between 20 and 40 minutes after injection to match the analysis performed in Lohmann et al (8).

Each study will be reviewed by a board-certified nuclear medicine physician and neuroradiologist within seven working days of the completion of the study, and a formal report will be dictated. This will be performed separately from the final analysis. The imaging findings on FET PET will be provided to the neurosurgeon and can be used in addition to MRI for planning of biopsy and surgery. For patients who received subsequent surgery, if possible the multi-parametric imaging examination will be used to target 1-4 tissue samples that have distinct metabolic findings for distinguishing recurrent disease from treatment effects.

If imaging is performed on a PET/MRI, a gadolinium-based contrast will be administered. The patient's eGFR will be checked and gadolinium will be administered per radiology department guidelines. The MRI protocol will include the clinical standard MRI. The MRI protocol may also contain research sequences such as novel sequences used for attenuation correction on PET/MRI (ie ZTE or zero echo time) and MRI spectroscopy sequences.

Optional repeat FET PET imaging will be offered to adult patients.

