6.1.1 Treatment Period

- FET administration and adverse event evaluation
 - Evaluation of adverse events 20 min after completion of imaging, \pm 60 min

- Vital signs
 - 20 min prior to administration of radiotracer, \pm 60 min
 - 20 min after completion of imaging, \pm 60 min
- Confirmation of negative pregnancy test (woman of childbearing potential only)

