7.2 Recording of an Adverse Event

All grade 3 and above adverse events will be recorded using the NCI CTCAE v4.0. The Investigator will assign attribution of the possible association of the event with use of the investigational drug.

| Relationship | Attribution | Description |
|--|-------------|--|
| Unrelated to investigational drug/intervention | Unrelated | The AE is clearly NOT related to the intervention |
| | Unlikely | The AE is doubtfully related to the intervention |
| Related to investigational drug/intervention | Possible | The AE may be related to the intervention |
| | Probable | The AE is likely related to the intervention |
| | Definite | The AE is clearly related to the intervention |

Signs or symptoms reported as adverse events will be graded and recorded by the Investigator according to the CTCAE. When specific adverse events are not listed in the CTCAE they will be graded by the Investigator as none, mild, moderate or severe according to the following grades and definitions:

| | |
|----------|---|
| Grade 0 | No AE (or within normal limits) |
| Grade 1 | Mild; asymptomatic or mild symptoms; clinical or diagnostic observations only; intervention not indicated |
| Grade 2 | Moderate; minimal, local, or noninvasive intervention (e.g., packing, cautery) indicated; limiting age-appropriate instrumental activities of daily living (ADL) |
| Grade 3: | Severe or medically significant but not immediately life-threatening; hospitalization or prolongation of hospitalization indicated; disabling; limiting self-care ADL |
| Grade 4: | Life-threatening consequences; urgent intervention indicated |
| Grade 5: | Death related to AE |

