Appendix 1 Schedule of Study Procedures and Assessments

| Schedule of Study Procedures and Assessments | | | | |
|---|------------------------------------|--------------------|---|-----------------------------------|
| Period/ Procedure | Screening (Day -30 to Day 1) | Imaging (Day 1) | Follow-up (Off-Study, Until biopsy, resection, or imaging) | Imaging ¹ (Day 30+) |
| Informed consent | X | | | |
| Pregnancy test (women of childbearing potential only) | | X | | X |
| Vital signs | | X ² | | |
| Imaging Procedure | | | | |
| FET administration | | X | | X |
| Sedation/anesthesia* | | X | | X |
| PET imaging | | X | | X |
| Adverse event reporting | | X ³ | | X ³ |
| Follow-up | | | | |
| Correlation with pathology, imaging | | | X | |

*sedation and anesthesia will be administered only in patients where it is required

¹ Optional study procedure

² Evaluation of vital signs 20 min prior to administration of radiotracer (± 60 min) and 20 min after completion of imaging (± 60 min)

³ Evaluation of adverse events 20 min after completion of imaging (± 60 min)

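### The safety endpoint runs to 48 hours at any grade, but the last scheduled adverse event check falls about 1 to 2 hours after injection and the grade-recording rule contradicts itself

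*Combined protocol and SAP*

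**What the plan says.** Section 2.2 sets the third secondary objective: "To assess the safety of FET PET, as determined by treatment emergent adverse events (TEAEs) within 48 hours of FET administration". The endpoint is the incidence of such events, the time frame is up to 48 hours, and no severity limit is given. The synopsis repeats the objective.

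Collection is described in several places:

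- Section 6.1.1 schedules "Evaluation of adverse events 20 min after completion of imaging", with a tolerance of ±60 minutes. Section 6.1.3 gives the same single time point for optional repeat imaging, and Appendix 1 matches both. Appendix 1 marks adverse event reporting on the imaging days and leaves it blank in the follow-up column.
- Section 5.2.1.1 has the tracer injected in the scanner and states that "imaging will last for 40 minutes".
- Section 3.6 adds that "there are no study specific related procedures that are required after the imaging study".
- Section 5.3 lists spontaneous patient reports among the safety parameters, and the synopsis says patients will be asked to report events. Neither gives a time or an end date.

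On grades, Section 7.2 opens with "All grade 3 and above adverse events will be recorded using the NCI CTCAE v4.0". Further down, the same section has the investigator grade and record whatever signs or symptoms are reported, with no floor, and supplies definitions of grades 1 and 2 for events not listed in the CTCAE. Appendix 2, item 3.1, requires grade 3 to 5 events to be entered in OnCore. Section 6 names REDCap as the data collection system and sets no grade floor for it.

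On vital signs, Appendix 1 has "Evaluation of vital signs 20 min prior to administration of radiotracer" and again 20 minutes after imaging, each ±60 minutes. The synopsis instead places them directly on either side of the injection.

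**The concern.** An incidence labelled as 48-hour will be read as the result of looking for events over 48 hours. Here the active look ends within an hour or two, and no call, visit or diary is planned afterwards. Events that start later enter the count only if a patient volunteers them.

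The second gap is severity. The endpoint covers any grade, yet one of the two rules in Section 7.2 begins at grade 3. A coordinator who follows that sentence would leave grade 1 and 2 events out of the numerator; one who follows the later sentence would include them.

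Both gaps push the reported rate down, that is, towards apparent safety. Section 1.1 says the trial is meant to supply safety and efficacy data for a New Drug Application, and this is its only safety endpoint.

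**Working it through.** The documents state no sample size, precision or expected rate for this endpoint, so there is no figure to reproduce. The check is arithmetic on the schedule.

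**Inputs.** Endpoint window: 48 h = 2,880 min (2.2). Imaging: 40 min from injection (5.2.1.1). Adverse event evaluation: 20 min after imaging ends, ±60 min (6.1.1, 6.1.3, Appendix 1).

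**Time of the evaluation** = imaging length + 20 min + tolerance.

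| Case | Sum | After injection | Share of 2,880 min |
|---|---|---|---|
| Earliest, read literally | 40 + 20 − 60 | 0 min | 0% |
| Nominal | 40 + 20 | 60 min | 2.1% |
| Latest | 40 + 20 + 60 | 120 min | 4.2% |

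At the latest permitted time, 48 − 2 = 46 hours remain with no scheduled collection.

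**Dependence on the 40 minutes.** Section 5.2.1.1 allows PET/MRI and gives no MRI duration. If imaging ends T minutes after injection, the latest evaluation is at T + 80 min. For that to reach even a tenth of the window (288 min), T would have to be 288 − 80 = 208 min. The percentages therefore move with session length, but the gap does not close.

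**Illustration of the undercount.** These inputs are assumptions, not document figures: N = 199 (planned enrolment, Section 3.3), at most one event per patient, no spontaneous reports, 25% to 75% of events starting before the evaluation, and 5% to 10% of events at grade 3 or above. Expected number captured = 199 × true rate × share starting in time × share recorded. Chance of recording none = (1 − recorded rate)^199.

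| Assumed true any-grade rate | Patients with an event | Captured, all grades recorded | Captured, grade 3+ only | Chance of recording none, grade 3+ only |
|---|---|---|---|---|
| 2% | 4.0 | 1.0 to 3.0 | 0.05 to 0.30 | 74% to 95% |
| 5% | 10.0 | 2.5 to 7.5 | 0.12 to 0.75 | 47% to 88% |
| 10% | 19.9 | 5.0 to 14.9 | 0.25 to 1.49 | 22% to 78% |

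Zero events in 199 patients gives a one-sided 95% upper bound of 1 − 0.05^(1/199) = 1.5%. That bound would apply only to the hours and grades actually covered.

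**Assessment windows.** Latest permitted pre-injection vital signs: −20 + 60 = 40 min after injection, whatever the imaging length. Earliest permitted post-imaging assessment: 40 + 20 − 60 = 0 min, at injection, if imaging takes 40 min (T − 40 min in general).

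**The case against.** Three stronger readings are tempting, and the documents support none of them.

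- *The endpoint cannot be measured.* It can, in part. Patients are asked to report events (synopsis), spontaneous reports count (5.3), all patients are evaluable from injection (7.1.1), and serious events are entered and reviewed (Appendix 2). Section 3.6 concerns follow-up for correlation with histology and does not end adverse event reporting. What stands is that the later route is passive, untimed and incomplete.
- *Recording is fixed at grade 3 and above.* Only the opening sentence of 7.2 says so, and a later sentence in the same section has no floor. Appendix 2 governs entry in OnCore, not the REDCap study data. The rule is contradictory rather than settled.
- *Most events will be grade 1 or 2, so most will be lost.* The documents give no expected grade profile. The severity shares used above are assumptions.

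It is also fair to say that the 0- and 120-minute limits rest on imaging ending at 40 minutes. The window overlap is a drafting flaw: the anchors themselves say before injection and after imaging, and no vital-sign endpoint depends on them. Finally, the endpoint is secondary and descriptive, with no threshold or success criterion attached.

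None of this supplies scheduled collection between the post-imaging check and 48 hours.

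**Conclusion.** The mismatch between endpoint and collection is real. Scheduled ascertainment ends nominally 1 hour and at latest about 2 hours after injection, 2% to 4% of the stated window, if imaging ends at 40 minutes; a longer session shifts this somewhat. As planned, the any-grade 48-hour incidence would be incompletely ascertained and probably under-counted, so a low observed rate could not be presented as 48-hour safety. The size of the undercount cannot be derived from the documents, and the table above only shows how it varies with assumed inputs.

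Section 7.2 must also be reconciled with itself and with the endpoint, because following its first sentence would remove grade 1 and 2 events. The overlapping ±60-minute windows are a lesser point: they conflict with the synopsis but do not by themselves undermine the endpoint. The trial's primary result is unaffected.

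**What to change.** Choose one of two routes for Section 2.2 and the synopsis:

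1. Restate the endpoint as adverse events observed up to the post-imaging assessment, plus any spontaneous reports. This is a wording change and needs no new contact.
2. Keep 48 hours and add one brief scripted contact at 48 hours after each administration, entered in Sections 6.1.1 and 6.1.3 and in Appendix 1. This costs a short coordinator contact per administration and a form field.

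With either route:

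- State in Section 7.2 that events of all grades are recorded in the study database for this endpoint. OnCore entry can stay at grades 3 to 5, as Appendix 2 has it.
- Make the windows in 6.1.1, 6.1.3 and Appendix 1 one-directional, so that pre-injection assessments finish before injection and post-imaging assessments start once imaging has ended, and align the synopsis wording on vital signs.

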| Primary Endpoints | 
 1) Sensitivity of FET PET using a CSOT (subject-level) 2) Specificity of FET PET using a CSOT (subject-level) |
| Duration of Therapy | The study will involve one imaging study involving FET PET for all patients. Adult patients may undergo repeat FET PET. |
| Duration of Follow up | Follow-up will be performed to correlate imaging findings with pathology. |
| Duration of study | The study will reach completion one year after completion of enrollment. |
| Study Drugs | Fluoroethyltyrosine (FET) |
| Safety Assessments | Patient vital signs will be taken immediately before and after the administration of the radiopharmaceutical. The patients will also be asked to report adverse events. |

List of Abbreviations

| | |
|--------|---|
| AE | adverse event |
| CHR | Committee on Human Research (UCSF IRB) |
| CSOT | Composite standard of truth |
| CT | computerized tomography |
| CTCAE | Common Terminology Criteria for Adverse Events |
| DSMC | Data and Safety Monitoring Committee |
| FDA | Food and Drug Administration |
| FDG | Fluorodeoxyglucose |
| FET | Fluoroethyltyrosine |
| FN | False Negative |
| FP | False Positive |
| HDFCCC | Helen Diller Family Comprehensive Cancer Center |
| ICH | International Council for Harmonisation of Technical Requirements for Pharmaceuticals for Human Use |
| IND | investigational new drug application |
| IRB | Institutional Review Board |
| MRI | magnetic resonance imaging |
| NCI | National Cancer Institute |
| NPV | Negative predictive value |
| PET | Positron Emission Tomography |
| PPV | Positive predictive value |
| PRC | Protocol Review and Monitoring Committee (UCSF) |
| RANO | Response Assessment in Neuro-Oncology |
| ROI | Region of interest |
| TBR | Tumor-to-brain ratio |
| TN | True Negative |
| TP | True Positive |
| TRC | Treatment-related changes |

Table of Contents

| | |
|---|----|
| Protocol Signature Page | 2 |
| Abstract | 3 |
| List of Abbreviations..... | 6 |
| Table of Contents..... | 7 |
| 1 Introduction..... | 13 |
| 1.1 Overview..... | 13 |
| 1.2 Background..... | 13 |
| 1.3 Patient Population..... | 14 |
| 2 Objectives of the Study | 14 |
| 2.1 Primary Objective..... | 14 |
| 2.2 Secondary Objectives | 15 |
| 2.3 Exploratory Objectives | 16 |
| 3 Study Design..... | 17 |
| 3.1 Characteristics..... | 17 |
| 3.2 Stopping Rules..... | 17 |
| 3.3 Number of Subjects | 17 |
| 3.4 Eligibility Criteria..... | 17 |
| 3.4.1 Inclusion Criteria | 18 |

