5.3 Monitoring and Toxicity Management

Each patient receiving FET will be evaluable for safety. The safety parameters include vital signs (heart rate and blood pressure) as well as physical findings and spontaneous reports of adverse events reported to the investigator by patients.

6 Study Procedures and Observations

Screening assessments must be performed within 30 days prior to the first dose of investigational product. Any results falling outside of the reference ranges may be repeated at the discretion of the investigator. Treatment or visit delays for public holidays or weather conditions do not constitute a protocol violation.

A written, signed, informed consent form (ICF) and a Health Insurance Portability and Accountability Act (HIPAA) authorization must be obtained before any study-specific assessments are initiated. A copy of the signed ICF will be given to the subject and a copy will be filed in the medical record. The original will be kept on file with the study records.

REDCap will be used to collect data for this study. REDCap is a secure, HIPAA-compliant, web-based system.

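### The safety endpoint covers 48 hours after FET, but the only scheduled adverse event check falls at most 2 hours after injection

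*Combined protocol and SAP*

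**What the plan says.** Section 2.2 sets the safety objective as "To assess the safety of FET PET, as determined by treatment emergent adverse events (TEAEs) within 48 hours of FET administration". Its endpoint is "Incidence of treatment-emergent adverse events (TEAEs"), with a time frame of up to 48 hours.

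The procedures are much shorter. Under section 5.2.1.1 the tracer is given while the "patient is in the PET scanner, and imaging will last for 40 minutes". Section 6.1.1 schedules one safety assessment, "Evaluation of adverse events 20 min after completion of imaging", and footnote 3 of Appendix 1 repeats it with its tolerance: "Evaluation of adverse events 20 min after completion of imaging (± 60 min"). Section 6.1.3 gives the same timing for optional repeat scans.

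After that, section 3.6 states that "there are no study specific related procedures that are required after the imaging study". The follow-up column of Appendix 1 contains only correlation with pathology and imaging.

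There are also passive routes. Section 5.3 counts "spontaneous reports of adverse events reported to the investigator by patients" as a safety parameter, and the Abstract says "The patients will also be asked to report adverse events". Neither gives a contact time or an end to the reporting period.

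**The concern.** An incidence over 48 hours needs some means of learning what happened in those 48 hours for each patient in the denominator. Here outpatients are asked once, shortly after the scan, and no later contact is planned. From then on, a patient who had no event and a patient who had one but did not call look the same in the data.

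The starting point is also weak. Section 7.1 does not define treatment-emergent, and Appendix 1 lists no symptom or adverse event question before injection. In patients with brain tumours, a headache reported at the single check may be new or long-standing, and the schedule does not provide the record needed to tell which.

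Section 1.1 gives prospective safety and efficacy data for a New Drug Application as the study's goal. A figure labelled as 48-hour incidence would claim more than the schedule measures, and events not elicited at the time cannot be reliably recovered later.

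**Working it through.** **Inputs**
- Endpoint window: 48 h = 2,880 min from administration (section 2.2).
- Injection in the scanner, imaging 40 min (section 5.2.1.1; the last reconstructed frame ends 40 min after injection).
- Adverse event check: 20 min after imaging ends, tolerance 60 min either way (section 6.1.1; Appendix 1, footnote 3).
- Required study procedures after imaging: none (section 3.6).

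The plan gives no coverage figure of its own to reproduce.

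**Time of the check after injection** = imaging duration + 20 min ± 60 min
- Nominal: 40 + 20 = 60 min
- Latest: 40 + 20 + 60 = 120 min
- Earliest, reading the tolerance literally: 40 + 20 − 60 = 0 min

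**Share of the window after the check** = (2,880 − t) / 2,880
- Nominal: 2,820 / 2,880 = 47/48 = 97.9%
- Latest: 2,760 / 2,880 = 46/48 = 95.8%
- Earliest: 2,880 / 2,880 = 100%

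So 95.8% is the minimum under the stated schedule.

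**If the session overruns.** Assuming imaging takes 60 or 90 min instead of 40, the latest check is at 60 + 80 = 140 min or 90 + 80 = 170 min. The share left is 2,740 / 2,880 = 95.1% or 2,710 / 2,880 = 94.1%. The conclusion does not depend on the exact scan length.

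**From time to events.** Let *e* be the share of 48-hour events that start before the check, all assumed to be found there, and *c* the share of later events that reach the study passively. Then observed / true incidence = *e* + (1 − *e*) × *c*.
- If every event starts early (*e* = 1), the ratio is 1 and nothing is lost.
- If onset is even over 48 hours, the check is at its latest time (*e* = 2/48) and nothing is reported passively (*c* = 0), the ratio is 4.2%.

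The documents give neither *e* nor *c*, so the size of the shortfall cannot be derived. Only its direction follows: the ratio cannot exceed 1.

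**Counting rules.** Section 9.2.1 defines the safety set as patients who completed initial imaging per protocol. Section 9.2.3 contains no analysis of the safety endpoint. Nothing states how a patient with no information after the check is handled.

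**The case against.** The strongest reply is that safety capture does not stop at the imaging-day check. Spontaneous reports are a named safety parameter (section 5.3), and patients are asked to report events (Abstract). Evaluability for toxicity starts at administration with no stated end (section 7.1.1). Each participant's status is discussed at monthly site committee meetings, and grade 3 to 5 and serious events are entered into the trial management system (Appendix 2). Related deaths are reportable for 30 days (section 7.4.1). The consent pages were not examined here and may add reporting instructions.

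This stands, and it limits the point. A reader might infer that nothing is collected after the check, or that patients who stay silent are counted as event-free. The documents support neither: passive capture exists, and no counting rule is stated. A reader might also turn 96% of the time into 96% of the events missed. That needs onset and reporting data which the plan does not contain, and events soon after injection would be missed less often.

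Nor can it be said that no pre-dose symptom record will exist. Sections 3.1, 3.4 and 5.2.1.1 mention baseline assessments or evaluations, and section 5.3 lists physical findings. The fair criticism is that their content is unspecified and Appendix 1 itemises no symptom inquiry.

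Passive capture still does not make the endpoint measurable as written. It has no contact schedule and leaves no record for those who do not report. It is also unclear for milder events: section 7.2 opens by requiring recording at grade 3 and above, then supplies definitions for grades 1 and 2, and Appendix 2 requires entry only from grade 3.

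**Conclusion.** The objective and the schedule do not match. At least 95.8% of the 48-hour window has no scheduled or solicited assessment, given 40 minutes of imaging and the stated tolerance. The resulting incidence is likely to be under-counted, assuming that some events begin after the check and that not all of them are volunteered. The documents do not allow the amount to be estimated.

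The unspecified pre-dose symptom record is a separate weakness. It makes treatment-emergent hard to apply to events that are found, and that error could run in either direction.

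This should be fixed, but it is not critical. The endpoint is secondary and descriptive, with no hypothesis or threshold, and the success criteria in section 9.2.2 do not depend on it.

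**What to change.** Reconcile objective 3 with Appendix 1 in one of two ways.

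- **(a) Narrow the endpoint.** Define it as treatment-emergent events from injection to the imaging-day check (at most 2 hours), and list later spontaneous reports separately. The tolerance should also be worded so that the check cannot fall at the moment of injection. This costs wording only, and the safety claim becomes narrower.
- **(b) Keep 48 hours.** Add one scripted remote query at or just after 48 hours to Appendix 1. Keep all dosed patients in the denominator and report the number not reached separately; restricting the denominator to those reached could selectively drop patients who are in hospital or have died. Section 9.2.1 would need to match, since it now requires completed imaging while section 5.3 makes every patient given FET evaluable. This costs a few minutes of coordinator time per patient and one case report form field. It can apply only to patients not yet imaged, so those already imaged should be reported under the shorter window.

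Under either option:
- ask the same symptom questions at the existing pre-dose vital-sign check, which adds no visit;
- define treatment-emergent as new or worsened after injection;
- reconcile the two parts of section 7.2 so that it is clear which grades are recorded and count towards incidence;
- state how patients without information for the full window are handled.
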